1.5.2. Viral Shedding Endpoint

Assuming the median time to cessation of viral shedding is 10 days, with a constant baseline hazard for cessation of shedding, 90% statistical power, 1-sided type I error rate of 2.5% for efficacy and early stopping for futility, the design (including interim analyses) can detect 60% or greater increase in the rate of shedding cessation in the combined high- and low-risk cohorts with 200 viral clearance events per pairwise comparison.

2. GENERAL DATA ANALYSIS CONSIDERATIONS

Descriptive statistics that will be used to summarize continuous variables are as follows: mean and standard deviation, median and interquartile range, quartiles, range, and number of missing data values. If applicable, continuous data that are skewed will be transformed to meet assumptions of normality. For categorical variables, descriptive statistics that will be used include the following: frequencies, relative frequencies, and the number of missing data values. Descriptive analyses summarizing baseline and follow-up data will be stratified by site and/or country. Line, scatter and box plots will be used, as appropriate, for longitudinal data representations. An alpha level of 0.05 will be used for all statistical tests unless otherwise specified.

2.1. BASELINE DATA

The following baseline variables will be described: age, sex, presence of known COVID-19 risk factors (includes all factors that categorize participants into the high-risk category), race/ethnicity and time since onset of symptoms.

Baseline variables will be summarized overall and within high and low risk strata by treatment arm. Because of the potential for imbalance between arms due to household-based randomization, statistical testing across arms will be performed using gee adjusted by risk strata with exchangeable correlation within household. If there appears to be imbalance across the arms, ($p<0.10$), the variable will be adjusted for in primary analyses.

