The Statistical Analysis Plan will be developed and finalized before database lock and will describe the participant populations to be included in the analyses, the detailed analytical plans with endpoints and procedures for accounting for missing, unused, and spurious data. An Interim Monitoring Plan will also be developed to describe approaches for re-estimation of sample size and any planned interim analyses. This section presents a brief summary of the planned statistical analyses of the primary and secondary endpoints (these are listed in [Section 4](#)).

11.3.1. *Efficacy Analyses*

Demographic characteristics (age, sex, race) of each study group will be tabulated.

The mean age (plus range and standard deviation) by sex of the enrolled participants, as a whole and per group, will be calculated.

Primary analyses: The primary analyses will be conducted on the intend-to-treat population overall and by cohort (high-risk and low-risk). Participants randomized to each active treatment will be compared to participants randomized to placebo (ascorbic acid). If appropriate, the primary analysis will make use of all participants randomized to placebo, whether contemporaneously enrolled or not, using an Empirical Bayesian information borrowing method (described below). Due to anticipated heterogeneity in risk of disease progression, pre-specified baseline variables, including age, BMI, and days of symptoms at time of enrollment will be included in the model to increase precision.

Both primary endpoints will be analyzed using a Cox proportional hazards model with robust standard errors, adjusted for within household correlation.

As-treated analysis: The primary analyses will be repeated, replacing randomization arm by actual treatment to account for possible off-label use of and noncompliance to the investigational products.

Subgroup analyses: All subgroup analyses will be pre-specified in the Statistical Analysis Plan. Any further subgroup analyses will be considered ad hoc.

Missing Data

Due to the design of the study and retention activities, measurable outcomes are expected for all participants. However, in the unlikely event of a missing test result, the missing data will be imputed.

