4. EFFICACY/EFFECTIVENESS ANALYSES

4.1. EFFICACY ANALYSES

All efficacy analyses will be adjusted for age, sex at birth and time from symptom onset to enrollment. These adjustments will be additive unless otherwise specified.

All analyses will account for the household clustering using robust standard errors as available. If not available, bootstrap methods will be used.

For time to event analyses, baseline (time 0) will be day of the enrollment visit.

Endpoints will be summarized as number of participants: hospitalized without prior LRTI, hospitalized with prior LRTI, died without prior LRTI, died with prior LRTI, who meet LRTI definition. These will be shown as counts and percentages overall and by cohorts defined in Section 2.2 within further breakdown by arm.

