4.1.1. LRTI objective

Objective: To test the efficacy of HCQ and HCQ + azithromycin compared to placebo to prevent progression to LRTI, among persons with SARS-CoV-2 infection who are at high risk of progression.

Outcome: LRTI, defined by resting SpO₂<93%, sustained for 2 readings 2 hours apart AND presence of subjective dyspnea or cough within the first 14 days of follow-up.

Cohorts: mITT LRTI Cohort

Data Sets: HCQ LRTI Efficacy Data Set, HCQ+A LRTI Efficacy Data Set

Definition of Endpoint: A participant will be defined as having the endpoint if they have two resting SpO₂ readings less than 93% two hours apart but not more than 48 hours apart AND report subjective dyspnea (defined as a response of “somewhat or higher” on the “trouble breathing” question on flupro) or cough (defined as “somewhat or higher” as self-reported wet or dry cough) within 24 hours of the time the SpO₂ is reported during the first fourteen days of follow-up. The event time will be recorded as the day of the first SpO₂ reading less than 93% with the presence of subjective dyspnea or cough. Participants who do not reach this endpoint will be censored at the last time that the endpoint was ascertained not to be present. Hospitalization or death due to COVID-19 may be a competing risk. Per FDA guidance, participants who are hospitalized or die due to COVID-19 will have an event time that is the first of LRTI, hospitalization or death.

Analysis Details:

Kaplan-Meier cumulative incidence curves will be estimated and plotted for each intervention including 95% confidence intervals accounting for household cluster.

Cox proportional hazards models stratified by site and adjusted for baseline covariates identified above will be used to estimate the efficacy as 1 minus the hazard ratio. Due to potential clustering induced by the household design, robust standard errors will be estimated for the hazard ratio. The overall efficacy will be tested using a p-value ascertained from the Wald statistic based on

Confidential

the robust standard error. 95% confidence intervals will also be calculated based on the robust standard error. If there are too few endpoints to fit a Cox model then the proportion of participants meeting the endpoint in the first 14 days will be reported. Each active arm will be compared to the control arm separately using Fisher's Exact test.

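### SAP 2.1 adds covariates to the primary Cox models on a p<0.10 baseline test, on top of a fixed list that omits BMI; the shedding model also omits the risk-cohort stratum

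*SAP*

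**What the plan says.** SAP 2.1 lists the baseline variables: "The following baseline variables will be described: age, sex, presence of known COVID-19 risk factors", followed by race/ethnicity and symptom duration. Because randomisation is by household, "statistical testing across arms will be performed using gee adjusted by risk strata with exchangeable correlation within household". The consequence, where a variable differs across arms at p<0.10, is that "the variable will be adjusted for in primary analyses".

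SAP 4.1 then states: "All efficacy analyses will be adjusted for age, sex at birth and time from symptom onset to enrollment". It also calls for household-robust standard errors, with the bootstrap as fallback.

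SAP 4.1.1 (LRTI) specifies "Cox proportional hazards models stratified by site and adjusted for baseline covariates identified above will be used to estimate the efficacy", and falls back to Fisher's exact test if events are too few. SAP 4.1.3 (shedding, high- and low-risk participants combined) takes over the 4.1.1 analysis by reference. SAP 4.1.2 (hospitalisation/death) uses Fisher's exact test only.

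Protocol 11.3.1 promises that "pre-specified baseline variables, including age, BMI, and days of symptoms at time of enrollment will be included in the model to increase precision". SAP 1.4 says randomisation was stratified by site and risk cohort.

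**The concern.** Under random allocation, a baseline p-value measures only how far chance has separated the arms. It carries no information on whether the variable predicts outcome, and that is what makes a covariate worth including. A rule keyed to it can bring in a useless variable and leave out a strong one.

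Part of the primary model is therefore settled only after baseline data are examined by arm. In a Cox model this matters for interpretation too, because the hazard ratio being estimated depends on which prognostic covariates are in the model.

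The rule is also not a closed algorithm. SAP 2.1 does not say whether risk factors are tested singly or as one variable, whether the comparison is three-way or pairwise among the three arms, or in which of the SAP 2.2 cohorts it is run. The reference in 4.1.1 to covariates given earlier could mean 2.1, 4.1 or both. Protocol 7.6.1 leaves the study statistician unblinded for analysis, so these choices should be closed in writing.

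Two related gaps sit beside the rule: BMI is missing from the fixed list, and risk cohort is missing from the shedding model's strata.

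**Working it through.** **1. The plan's own figure.** SAP 1.5.2 gives 200 clearance events per pairwise comparison for a rate ratio of 1.6, 90% power and one-sided 2.5%; SAP 1.5 adds four interim looks and a final analysis.

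- Schoenfeld, fixed design: 4(1.960 + 1.282)² / (ln 1.6)² = 42.03 / 0.2209 = 190.3, so 191.
- Freedman: (1.960 + 1.282)² × (2.6/0.6)² = 10.51 × 18.78 = 197.3, so 198.
- Five O'Brien-Fleming looks need about 3% more than Schoenfeld: 190.3 × 1.03 = 196.

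The 200 reproduces to within about 3%. It does not depend on the covariates.

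**2. How many variables the rule can add.** Of the five items in SAP 2.1, age, sex and symptom duration are already fixed by 4.1, so their p-values change nothing. That leaves risk factors and race/ethnicity: 2 candidates if risk factors are one summary variable. If they are tested singly there are 7: the seven criteria in Protocol 6.1, less age, plus race/ethnicity.

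**3. Chance of a spurious addition.** For k independent candidates balanced by randomisation, it is 1 − 0.9^k.

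- k = 2: 1 − 0.81 = 19%.
- k = 7: 1 − 0.478 = 52% (53–54% in the simulation below).

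**4. Effect on error rate, standard error and power.** Simulated Cox model: 165 per arm (SAP 1.5.1), control median 10 days, censoring at day 14, 5% dropout, household-robust standard errors, 6,000 null and 3,000 alternative runs per scenario.

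The documents give no covariate effects or household rate, so these are assumptions:
- log hazard ratios per SD of 0.2 (weaker) or 0.4 (stronger) for age and symptom duration, and 0.3 for sex;
- 0.4 or 0.8 for three of seven binary candidates, and none for the other four;
- about 10% of participants in two-person households.

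A household-robust z test stood in for the GEE. Site strata and interim looks were not modelled.

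| Model | Rejection under no effect, weaker / stronger | Power at rate ratio 1.6, weaker / stronger |
|---|---|---|
| Three fixed covariates only | 5.0% / 5.3% | 90.7% / 82.3% |
| Fixed three plus p<0.10 additions (SAP rule) | 4.9% / 4.9% | 91.1% / 84.0% |
| p<0.10 rule with no fixed list | 4.6% / 4.3% | 89.3% / 77.6% |
| All ten covariates fixed in advance | 5.5% / 6.0% | 92.1% / 90.5% |

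Monte Carlo standard error is about 0.3 points under the null and 0.5 to 0.8 points for power.

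- SAP rule, mean estimated SE against empirical SD under the null: 0.1438 vs 0.1432 and 0.1453 vs 0.1443, within 1%.
- Power gap to the ten-covariate model: 92.1 − 91.1 = 1.0 point and 90.5 − 84.0 = 6.5 points. Part may be inflated, because that model's null rate is slightly high.
- Mean log hazard ratio at a true value of ln 1.6 = 0.470: SAP rule 0.446 / 0.407; ten covariates 0.468 / 0.465. The estimate moves with the covariate set.

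**5. Lists and strata side by side.**

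- Protocol 11.3.1: age, BMI, symptom duration (an open list). SAP 4.1: age, sex, symptom duration. In the SAP, BMI can enter only as a risk factor that happens to be imbalanced, and the cut-off differs: above 30 in the low-risk definition of SAP 2.2, 35 or more in Protocol 6.1.
- Randomisation strata: site and risk cohort. Shedding model: site only, with cohorts combined. SAP 7.3 (symptom resolution) does stratify by risk. The p<0.10 test is itself adjusted for risk strata, so it cannot be relied on to bring risk cohort in.

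**The case against.** The best defence is that the rule is written in advance, is mechanical, sits on top of a sensible fixed list, and has a stated reason: household randomisation can leave larger imbalances. Much of this stands. Two of the protocol's three named covariates are always in the model, and the hospitalisation/death endpoint is untouched. LRTI may fall back to Fisher's test, since the trial stopped for operational futility on the clinical objectives (SAP 1.3). Shedding is the main endpoint exposed.

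The household argument does not rescue the rule. Households are still allocated at random, and clustering is already handled by the robust standard errors. A test that allows for clustering still flags about 10% of balanced variables.

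A reader might infer three stronger things that the documents do not support:

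- That significance testing replaces the pre-specified list. SAP 4.1 rules this out.
- That p-values and intervals are wrong. The mild conservatism (4.6% / 4.3%) appears only if the rule stands alone; under the SAP rule type I error was 4.9%.
- That the rule costs power. Against the fixed list alone no loss was seen (91.1% vs 90.7%; 84.0% vs 82.3%).

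The BMI mismatch may also partly reflect versions: the SAP covers the HCQ arms, while the supplied protocol centres on LPV/r and leaves detail to the SAP.

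**Conclusion.** The point holds in a limited form. Part of the primary Cox model, chiefly for shedding, is chosen by chance imbalance and is not known in advance; the chance of at least one spurious addition is 19% to 52%, depending on how the risk factors are coded. These figures assume independent candidates.

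No material error in type I rate or standard errors is shown. The 1 to 6.5 point power shortfall rests on assumed covariate effects and applies only against fixing all ten simulated covariates. It is not an estimate of the gain from the change below, which adds only BMI and the risk stratum; that gain was not calculated.

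The omission of risk cohort from the shedding model and the undefined covariate reference in SAP 4.1.1 stand on the SAP text alone. The BMI discrepancy stands subject to the version caveat. The change is worth making because it closes the primary model at almost no cost.

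**What to change.** - Delete the p<0.10 rule from SAP 2.1 and present baseline tables without tests. An imbalance-driven adjustment can be kept as a labelled sensitivity analysis.
- State one list for the Cox primary models: age, sex at birth, symptom duration, and BMI in the form collected, reconciled with Protocol 11.3.1. Give a reason if BMI is left out.
- Say in SAP 4.1.1 that the covariates referred to are that list.
- Stratify the shedding model in SAP 4.1.3 by site and risk cohort. Risk cohort does not apply to the LRTI model, which is restricted to high-risk participants.
- Leave the Fisher's exact analyses as they are.

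The cost is SAP wording. The one open item is BMI: the documents show a self-reported threshold (Protocol 6.1) but do not confirm that a continuous value was recorded. If only the threshold exists, use the indicator and say so.

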2.2. ANALYSIS COHORTS AND DATA SETS

This section describes the cohorts and corresponding datasets for the primary, secondary and exploratory analyses described in this document. In the definitions below, cohort refers to the study participants included in a dataset; whereas the datasets further specify which visits are included from the specified cohort. All data sets include the baseline variables specified in Section 2.1 and are included as guidance, recognizing that in practice, what is listed as a single data set may actually require sets of data sets (for example repeated vs single time point outcomes for secondary outcomes) depending on the analysis.

Intention to Treat (ITT) Cohort: The ITT Cohort includes all participants enrolled into the study.

Modified Intention to Treat (mITT) Cohort: The mITT Cohort includes all participants enrolled into the study who completed the day 1 (enrollment) questionnaire.

Viral Shedding (VS) Data Set This data set will include all participants in the cohort with all data required for primary and secondary viral shedding endpoints.

Hydroxychloroquine (HCQ) Secondary Efficacy Data Set This data set will include all participants in the cohort randomized to hydroxychloroquine or contemporaneous control and secondary endpoints.

Hydroxychloroquine + azithromycin (HCQ+A) Secondary Efficacy Data Set This data set will include all participants in the cohort randomized to the combination hydroxychloroquine/azithromycin arm or its contemporaneous control and secondary endpoints.

Hydroxychloroquine (HCQ) Safety Data Set This data set will include all participants in the cohort randomized to hydroxychloroquine or contemporaneous control and secondary outcomes.

Hydroxychloroquine + azithromycin (HCQ+A) Safety Data Set This data set will include all participants in the cohort randomized to the combination hydroxychloroquine/azithromycin arm or its contemporaneous control and safety outcomes.

Hospitalized Data Set This data set will include all participants who reported a COVID-19-related hospitalization within the planned 28 days of follow-up.

Modified Intention to Treat (ITT) High Risk (HR) Cohort: The ITT HR Cohort includes all mITT cohort participants enrolled into the study's high risk cohort.

Hydroxychloroquine (HCQ) Efficacy Data Set This data set will include all participants in the cohort randomized to hydroxychloroquine or contemporaneous control.

Hydroxychloroquine + azithromycin (HCQ+A) Efficacy Data Set This data set will include all participants in the cohort randomized to the combination hydroxychloroquine/azithromycin arm or its contemporaneous control.

Intention to Treat (ITT) Low Risk (LR) Cohort: The ITT LR Cohort includes all contacts enrolled into the study's low risk cohort (persons age 18-59 without risk factors for severe disease, including pulmonary disease, DM1 or DM2, HTN, immunocompromising condition, or BMI>30)).

Modified Intention to Treat (mITT) LRTI Cohort: The mITT LRTI cohort includes ITT HR Cohort participants who did not meet the criteria for the primary LRTI endpoint on day 1. The following data sets are created from participants in this cohort.

Hydroxychloroquine (HCQ) LRTI Efficacy Data Set This data set will include all participants in the cohort randomized to hydroxychloroquine or contemporaneous control.

Hydroxychloroquine + azithromycin (HCQ+A) LRTI Efficacy Data Set This data set will include all participants in the cohort randomized to the combination hydroxychloroquine/azithromycin arm or its contemporaneous control.

Modified Intention to Treat (mITT) Disease Resolution Cohort: This cohort includes mITT Cohort participants who meet the COVID-19 disease criteria on day 1 (Section 7.3). The following data sets are created from participants in this cohort.

Hydroxychloroquine (HCQ) Disease Resolution Data Set This data set will include all participants in the cohort randomized to hydroxychloroquine or contemporaneous control.

Hydroxychloroquine + azithromycin (HCQ+A) Disease Resolution Data Set This data set will include all participants in the cohort randomized to the combination hydroxychloroquine/azithromycin arm or its contemporaneous control.

Modified Intention to Treat (mITT) Viral Shedding Cohort: This cohort includes mITT Cohort participants who do not meet the definition for clearance of viral shedding at baseline (day 1 and day 2 negative swabs). The following data sets are created from participants in this cohort.

Hydroxychloroquine (HCQ) Viral Shedding (VS) Data Set This data set will include all participants in the cohort randomized to hydroxychloroquine or contemporaneous control.

Hydroxychloroquine + azithromycin (HCQ+A) Viral Shedding (VS) Data Set This data set will include all participants in the cohort randomized to the combination hydroxychloroquine/azithromycin arm or its contemporaneous control.

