- Complete the Exit Contact Survey (online, telephone, or text messaging). This survey will include confirmation of adherence to study therapy dosing and daily swab collection, concomitant medication review, AEs, and symptoms review and objective measures including SpO₂, temperature, and pulse. In addition, the modified Flu-PRO and WHO Ordinal Scale for Clinical Improvement surveys will be completed.
- *If in DBS sub-study, collect DBS sample for analysis of HCQ, azithromycin, or LPV/r concentrations as well as detection of anti-SARS-CoV-2 antibodies.*

For participants who are hospitalized on Day 28, the Day 28 procedures will be performed within 3 days after discharge from the hospital.

A study team member will be available via Telehealth, text messaging, or telephone to provide support for completion of study procedures.

The courier will collect the swabs at minimum within 1 or 2 days of Day 28.

Clinical outcomes will be confirmed through the electronic health record, if possible.

Participant Reimbursement

Participants will be reimbursed on Day 28 or at the post discharge visit. No reimbursement will be provided for unscheduled Telehealth visits requested by the participants for support with study procedures.

10. Study Assessments and Procedures

- Study procedures and their timing are summarized in the SoA.
- Protocol waivers or exemptions are not allowed.
- Immediate safety concerns should be discussed with the Sponsor immediately upon occurrence or awareness to determine if the participant should continue or discontinue study treatment.
- Adherence to the study design requirements, including those specified in the SoA, is essential and required for study conduct.
- All baseline evaluations must be completed and reviewed to confirm that potential participants meet all eligibility criteria. The Investigator will maintain a screening log to record details of all participants screened and to confirm eligibility or record reasons for screening failure, as applicable.
- Procedures conducted as part of the participant's routine clinical management and obtained before signing of the informed consent form may be utilized for screening or baseline purposes provided that the procedures met the protocol-specified criteria and were performed within the time frame defined in the SoA.

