11.1.1. COVID-19 Endpoints

Overall sample size will depend on the number of events observed. To detect at least a 1.5-fold increased risk of the COVID-19 symptom resolution rate under a null hypothesis of no reduction

and four interim monitoring analyses with stopping for futility and efficacy based on the O'Brien-Fleming bounds and 80% power, the trial is designed to achieve 99 events per pairwise comparison for the symptom resolution endpoints. To achieve this, 173 participants will be enrolled per arm.

As the initial sample size target, 210 per arm was chosen for each experimental group (HCQ, HCQ + azithromycin), assuming a control arm rate of approximately 30% and 5% dropout rate.

HR (active/control)	Events/arm	N per arm	Median control arm (days)	Median active arm (days)*
1.4	142	247	10	7
1.5	99	173	10	7
1.6	75	129	10	6
1.7	59	103	10	6
1.8	49	85	10	6
1.9	41	71	10	5
2,0	36	63	10	5

*Under constant baseline hazard assumption

11.1.2. *Viral Shedding Endpoint*

Assuming the median time to cessation of viral shedding is 10 days and a constant baseline hazard for cessation of shedding, approximately 62% of participants would no longer experience viral shedding at 14 days under the null hypothesis of no intervention effect. Assuming 420 participants per pairwise comparison, 90% statistical power, 1-sided type I error rate of 2.5% for efficacy, we can detect at least a 37% increase in the rate of cessation of viral shedding. Under an extreme example of having only half that sample, 210, we could detect an increase of 54% or higher.

11.2. *Populations for Analyses*

For analysis purposes, the following populations are defined and will be described in greater detail in the trial Statistical Analysis Plan:

Population	Description
Intention to Treat (ITT)	All enrolled participants
Modified ITT	All enrolled participants who do not have LRTI at Baseline: high-risk group for the primary clinical endpoint; high- and low-risk groups (separately) for the primary virologic endpoint.
PK evaluable	Participants from the DBS sub-study with at least 1 interpretable PK sample.

DBS: dried blood spot; PK: pharmacokinetic; PCR: polymerase chain reaction; SARS-CoV-2: severe acute respiratory syndrome coronavirus 2.

11.3. *Statistical Analyses*

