4.1.2. Hospitalization/Death objective

Objective: To test the efficacy of HCQ, HCQ + azithromycin, or LPV/r compared to placebo to prevent hospitalization and death measured at Day 28 among participants who are at high risk of progression

Outcome: COVID-19 related hospitalization or death at or before day 28 or follow-up

Cohort: mITT High Risk Cohort

Data sets: HCQ Efficacy Data Set, HCQ+A Efficacy Data Set

Definition of Endpoint: A participant will be defined as having the endpoint if they were hospitalized or died due to COVID-19 as determined by the adjudication committee before day 28.

Analysis Details:

The proportion of participants with a hospitalization or death before the end of planned follow-up will be reported. Each active arm will be compared to the control arm separately using Fisher's Exact test.

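### All three SAP primary analyses require a completed Day 1 questionnaire, a post-randomisation condition found in neither protocol population, and no ITT test of a primary endpoint is planned

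*SAP*

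**What the plan says.** **Protocol.** Section 11.3.1 states: "The primary analyses will be conducted on the intend-to-treat population overall and by cohort (high-risk and low-risk"). Section 11.2, immediately before it, defines a modified ITT and links it to the primary endpoints: "All enrolled participants who do not have LRTI at Baseline: high-risk group for the primary clinical endpoint", with both risk groups, separately, for the virologic endpoint. Section 11.2 leaves further detail on populations to the SAP.

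**SAP 2.2.** ITT is everyone: "The ITT Cohort includes all participants enrolled into the study". The modified ITT is narrower: "The mITT Cohort includes all participants enrolled into the study who completed the day 1 (enrollment) questionnaire". The high-risk cohort carries an ITT abbreviation but is a subset of the modified ITT: "The ITT HR Cohort includes all mITT cohort participants enrolled into the study's high risk cohort". The LRTI cohort is that high-risk cohort minus participants meeting the LRTI criteria on Day 1. The viral shedding cohort is the modified ITT restricted to "participants who do not meet the definition for clearance of viral shedding at baseline (day 1 and day 2 negative swabs").

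**Use in the primary objectives.** SAP 4.1.1 (LRTI) uses the mITT LRTI cohort. SAP 4.1.2 (hospitalization/death) specifies "Cohort: mITT High Risk Cohort". SAP 4.1.3 (shedding) uses the mITT viral shedding cohort. ITT is kept for safety (section 6), hospitalization duration (7.1) and disease severity (7.2). The updates listed in SAP 1.3 do not mention a change of population.

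**The concern.** Randomisation protects a comparison only if membership of the analysis set cannot depend on what happens afterwards. Whether someone completes a Day 1 survey can depend on early deterioration, on receiving the study supplies, or on tolerance of the first doses. A participant admitted to hospital before completing it would leave the hospitalization/death analysis even though the outcome is adjudicated and might be known from records.

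The shedding cohort raises a second, narrower issue: part of its entry rule is a swab taken after dosing has begun.

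At stake is whether the reported primary comparisons are the randomised ones, in a trial with very few hospitalizations, where single events carry weight.

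**Working it through.** **Step 1: which filter applies to which primary objective**

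| Objective | Protocol 11.3.1 | Protocol 11.2 mITT | SAP cohort | In neither protocol population |
|---|---|---|---|---|
| LRTI (4.1.1) | ITT | No LRTI at baseline | mITT, high-risk, no LRTI on Day 1 | Questionnaire |
| Hospitalization/death (4.1.2) | ITT | No LRTI at baseline | mITT, high-risk | Questionnaire |
| Shedding (4.1.3) | ITT | No LRTI at baseline | mITT, not negative on both Day 1 and Day 2 | Questionnaire and swab rule |

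The baseline-LRTI exclusion has support in Protocol 11.2. The questionnaire and swab rules have none.

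**Step 2: timing.** Protocol 9.1 randomises after the Day 0 checks and then sends the kits. The swab, survey and first doses follow on Day 1. Day 0 and Day 1 may share a date, but the order holds. So survey completion is a post-randomisation event and the Day 2 swab is on treatment. The Day 1 swab is listed before dosing, but no text says it must be taken before dosing.

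**Step 3: questionnaire filter.** The documents give no completion rate. Assuming 5-10% non-completion and the SAP 1.5.1 target of 165 per arm: 0.05 × 165 ≈ 8 and 0.10 × 165 ≈ 17 leave per arm. The trial stopped early, so actual counts would differ.

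Sensitivity of the Fisher test, with assumed counts:

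- 6/100 vs 0/100 gives two-sided p = 0.029.
- Dropping one participant per arm, one of them with an event, leaves 5/99 vs 0/99, p = 0.059.

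This is a near-threshold case. With 60, 100 or 165 per arm, p < 0.05 needs at least 6 events against 0, or 8 against 1.

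**Step 4: the Day 1/Day 2 rule.** SAP 4.1.3 dates clearance to the first negative swab, so those removed would otherwise be Day 1 events. Let p1 be the share negative on Day 1 and q the share of those negative again on Day 2. The number excluded per arm is 165 × p1 × q. Assume p1 = 5-20% and q = 60-80% in control, and let the SAP 1.5.2 effect (rate ratio 1.6) act on the Day 2 swab: q(treated) = 1 − (1 − q)^1.6, that is 0.769 for q = 0.6 and 0.924 for q = 0.8.

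| p1 | q control | Excluded, control | Excluded, treated | Difference (percentage points) |
|---|---|---|---|---|
| 5% | 0.6 | 5.0 | 6.3 | 0.85 |
| 5% | 0.8 | 6.6 | 7.6 | 0.62 |
| 10% | 0.6 | 9.9 | 12.7 | 1.69 |
| 10% | 0.8 | 13.2 | 15.2 | 1.24 |
| 20% | 0.6 | 19.8 | 25.4 | 3.38 |
| 20% | 0.8 | 26.4 | 30.5 | 2.48 |

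A simulation with median clearance of 10 days, constant hazard and follow-up to Day 14 gave these event-rate ratios:

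- True ratio 1.6: 1.51-1.55 in all randomised, about 1.555 after the exclusion.
- No drug effect: 1.00 both ways.

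**Step 5: power.** For the 200 shedding events of SAP 1.5.2 at ratio 1.6, the Freedman formula gives 198 and the fixed-design Schoenfeld formula 191. Losing 5%, 10% or 15% of the 200 lowers fixed-design power from 91.4% to 90.0%, 88.4% or 86.5%. Lost power is not the main issue.

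**The case against.** **The protocol is not a clean ITT plan.** A reader might infer that the SAP overrode one. It did not: Protocol 11.2 assigns its own modified ITT to the primary endpoints and defers detail to the SAP, so 11.2 and 11.3.1 already disagree. This stands, and it limits the conflict to the questionnaire and swab rules.

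**The documents are from different stages.** The SAP covers the HCQ, HCQ + azithromycin and control arms; the supplied protocol is the later LPV/r version with different clinical endpoints. Its ITT sentence speaks of each active treatment, but the HCQ-era wording cannot be seen. This stands as an assumption.

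**Early clearers are not removed in general.** A reader might infer that the shedding rule discards people who clear early on active drug. Removal needs negative swabs on both Day 1 and Day 2. Anyone positive on Day 1 who clears from Day 2 onward stays in and counts. The rule is largely an at-risk condition, and its simulated effect is small.

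**Visible pill differences are a weak mechanism here.** Protocol 7.6.1 says HCQ and ascorbic acid look alike, and that azithromycin and folic acid share a schedule but differ in shape. The explicit statement of dissimilarity concerns LPV/r, which this SAP does not analyse.

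**Events do not vanish from reporting.** SAP 6 and 6.2 tabulate hospitalizations and deaths as SAEs on ITT, SAP 4.1 gives counts for every cohort, and SAP 3.1 reports numbers with data for each endpoint. This stands. What is missing is the formal test on the randomised set.

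**Health records may not cover everyone.** Protocol 9.5 says only: "Clinical outcomes will be confirmed through the electronic health record, if possible". So outcomes cannot be assumed available for all non-completers. That is a reason to report missing outcomes by arm, not to exclude everyone without a survey.

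**Conclusion.** The point holds in limited form. All three SAP primary objectives carry a post-randomisation inclusion condition that appears in neither protocol population, and no ITT test accompanies them. It matters most for hospitalization/death, where the endpoint does not depend on the questionnaire. For shedding, the two-swab rule lets an on-treatment result decide inclusion for participants negative on Day 1; under the assumed rates it shifts the rate ratio by at most about 0.045 (1.51 to 1.555) and not at all under no effect. That null result depends on Day 2 negativity being equal between arms when the drug is inert.

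The documents show a possible route for selection. They do not show that it occurred, differed by arm or changed a result, and they give no figure from which its size can be computed. The conclusion assumes that the Protocol 11.3.1 sentence also applied to the HCQ arms. Even without that, the SAP's own ITT definition is applied to no primary objective, and the term modified ITT means different things in the two documents.

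**What to change.** 1. Reconcile Protocol 11.2, Protocol 11.3.1 and SAP 2.2 so that each primary endpoint has one named population, and give the modified-ITT high-risk cohort a label that does not read as ITT.
2. Run the hospitalization/death Fisher's exact test on all randomised high-risk participants as the primary analysis, using adjudicated outcomes and health records where available. Report unknown outcomes by arm.
3. Drop the questionnaire condition from the LRTI and shedding primary cohorts. Base any baseline-LRTI exclusion on data collected before dosing.
4. For shedding, include all randomised participants. Base any baseline exclusion only on a swab confirmed to be pre-dose, and censor those with no swabs at time 0. They add no information to the Cox model, but they stay visible in the denominators.
5. Keep the current modified-ITT cohorts as sensitivity analyses, and report exclusions by arm and reason.

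Cost: SAP wording, one extra set of runs, and slight dilution from participants who never started treatment. Excluding on a single pre-dose negative swab would remove more people than the two-swab rule: 165 × 5-20% ≈ 8-33 per arm, against 5-26 in control under the same assumptions. That loss would be unrelated to treatment, and making no baseline swab exclusion avoids it.
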